**DOCUMENT HISTORY**

Version	Date	Description of Change	Brief Rationale
1.0	19-Oct-2017	Initial Release	N/A
2.0	20-Mar-2018	Section 4.1: Grammatical edit	Grammatical edit
		Section 5.2: Add exclusion criteria	Protect vulnerable populations (pediatric, pregnant, and psychiatric patients) and exclude Emergency Room, where catheter care is not routinely performed due to short length-of-stay in unit
		Sections 6.1 & 6.2: Revision to training procedures	Explicitly states who will be trained, who is responsible for any training during study, and what materials and equipment will be provided.
		Section 6.3 & 9.1.3: Clarification on database access	Clarification to indicate the sponsor may need access to the master linking list with participant IDs and names in the event of an Adverse Event or other situation. The database will still be housed at NorthShore.
		Section 6.3.1.1: a) Edits to data collection process, b) variables conducted and c) reference to the Case Report Form that can be found in Appendix 11.2.	A) The use of REDCap for electronic CRF capture is no longer an option. Paper CRFs will be created to comply with regulatory requirements and then transferred to an electronic database. B) Certain variables could not be collected for the retrospective group, so these have been updated as well. C) A copy of the paper CRF is referenced in this section, and can be found in Appendix 11.2.
Section 6.3.1.1.3: Edits to the process for collecting healthcare professional feedback on the product.	Clarifies the process for data collection and stresses that participation is strictly voluntary with no impact on employment. A copy of the email that will be sent to potential participants is provided in Appendix 11.7.		

		Section 6.3.1.2: Edit to retrospective data collection process.	Indicate that retrospective data will also be collected using the paper Case Report Form.
		Section 6.3.2: Edit to the compliance process	Compliance will be measured via the internal audits rather than a count of all product used.
		Section 8.2.1: edit to statistical analysis plan and methods for primary endpoint	Minor edits to provide more detail and clarity
		Section 8.2.3.1: Edit to analysis plan of healthcare professional feedback	Indicate these data will be analyzed while study is ongoing
		Section 9.1.4: Edits to Personnel	Inclusion of additional staff members
		Section 9.1.7.1: Edits to data management	Change from REDCap system to paper Case Report Form system
		Appendix 11.5: Case Report Form replaces previous material.	Case Report Form added now that data collection will be in paper form
		Appendix 11.6: Case Report Form for urine culture sub-analysis	Provide separate Case Report Form for this portion of the study since it will only entail a small sub-sample of the study sample.
		Appendix 11.7: Sample e-mail to NorthShore employees for participation in feedback portion of study.	Provide IRB with direct language for communication to NorthShore employees
3.0	31-Jul-2018	Appendix 11.1.3	Updated instructions for use for ReadyBath Intelligent Warmer as a different model is to be used for the study.
4.0	02-Jan-2019	6.1: Events Prior to Intervention	Clarify typographical error to Nurse Educators
		6.3.1.2: Retrospective Data Collection	Clarify retrospective data collection to reflect that only in-depth details will be collected for subjects that developed a CAUTI

		8.2.1: Primary Endpoint	Modification of analysis plan due to change in data collected (modification took place before looking at data)
		Section 9.1.4: Key Roles and Study Governance	Removed all titles and responsibilities for NorthShore and Sponsor Staff; only Principal Investigator information will remain.
		Section 9.1.7.1: Data Collection and Management Responsibilities	Clarify CRF data collection for prospective and retrospective portions.
5.0	19-Dec-2019	Months were replaced with catheter days.	Changes in the timeline due to extension of the study.
		Addition in Section 6.3.2: Compliance with Intervention/Auditing.	Updated the information in section 6.3.2 regarding second set (and subsequent, if required) of audits.
		Addition of Section 11.1.4: ReadyBath ® Intelligent Warmer	Included the older (section 11.1.3) and the newer (section 11.1.4) warmers, with their instructions for use (IFU), in this protocol. Some of the older warmers may be replaced with the newer version, as they malfunctioned and the manufacturer has discontinued the older warmer.

## 1. PROTOCOL SYNOPSIS

Title:	Efficacy of Meatal and Perineal Care with a Prepackaged Cleansing Cloth and Standardized Cleansing Protocol in Reducing Catheter-Associated Urinary Tract Infections in Acute-Care Hospitals
Study Description:	A single-site, open-label, superiority study evaluating the efficacy of a prepackaged cleansing cloth and standardized cleansing protocol vs. current standard-of-care for catheter care and maintenance.
Objective:	Reduction in CAUTIs following implementation of prepackaged cleansing cloth and standardized cleaning protocol for all indwelling urinary catheter (IUC) care and maintenance, relative to current standard-of-care for the site.
Endpoint:	Incidence of CAUTI during intervention period compared to historical rate prior to intervention period.
Study Population:	Adult male and female patients who have an IUC inserted during their hospitalization at a northern suburban Chicago hospital system comprised of four acute-care hospitals. The study is powered to achieve a certain number of catheter days rather than participant number; prospective data collection will occur until all expected catheter days (42,672) have been completed.
Phase:	Post-market
Description of Sites/Facilities Enrolling Participants:	A hospital system composed of four acute-care facilities in the northern Chicago suburbs
Description of Study Intervention:	A pre-packaged, pH balanced, hypoallergenic cleansing cloth with a standardized cleaning protocol for IUC care and maintenance.
Study Duration:	The study will last until all expected catheter days (42,672) have been completed, and all data have been analyzed.
Participant Duration:	Participant duration will vary in length depending on how long they have an IUC inserted.

## 2. INTRODUCTION

### 2.1. Study Background and Rationale

Catheter-associated urinary tract infections (CAUTI) are one of the most common hospital-acquired infections (HAI), accounting for more than 15% HAIs in the United States. On October 1, 2008, the Centers for Medicare & Medicaid Services (CMS) stopped reimbursing hospitals for treatment of preventable HAIs. Subsequently, hospitals have implemented CAUTI prevention bundles to reduce these largely preventable, costly, and morbid infections. Guidelines for the prevention of CAUTI focus on the following four aspects of prevention: appropriate device utilization, aseptic insertion technique, proper care/maintenance of the catheter, and timely removal of the urinary catheter.

Several interventions seeking to reduce CAUTIs have studied the impact of chlorhexidine gluconate (CHG) bathing in the intensive care unit (ICU) but have not found a significant effect. Though one study did find a significant reduction in high-level (>50,000 colony-forming units) candiduria and any level of bacteriuria with CHG bathing, the study did not evaluate the impact on CAUTI rates, nor did it investigate the effect of perineal care and maintenance following catheter insertion. Additionally, the expanded use of CHG carries with it the potential for development of CHG-resistant bacteria which could compromise its use for surgical site infection prevention.

Few studies have exclusively investigated the effect of catheter care and maintenance on CAUTI rate. ReadyCleanse® meatal and perineal cleansing cloth by Medline Industries, Inc. (hereafter ReadyCleanse®) is a set of five prepackaged cloths including a gender-specific, five-step cleansing process clearly described on label that is designed to minimize transfer of bacteria to the patient during catheter care. Moreover, it does not contain ingredients that are bactericidal or bacteriostatic, thereby reducing the risk of compromising interventions such as CHG prior to surgery due to overuse. Thus, ReadyCleanse® provides an easy-to-use, efficient, and standardized means of conducting catheter care that may significantly reduce CAUTI rates compared to standard-of-care.

### 2.2. Risk/Benefit Assessment

ReadyCleanse® cloths are currently marketed products in the United States that are intended for meatal and perineal care, including when a patient has an indwelling urinary catheter (IUC) inserted. In this study, ReadyCleanse® cloths will be used strictly in accordance with their current labeling. ReadyCleanse® cloths were evaluated for safety through a repeat insult patch testing (RIPT) study in adults and a pediatric safety in use study. Based on the results of the RIPT study, it was concluded that ReadyCleanse® cloths did not have potential for eliciting dermal irritation or inducing sensitization. Based on the results of the pediatric safety in use study, it was concluded that ReadyCleanse® cloths did not demonstrate a potential to cause skin irritation for the study duration. Taken together, the risk to patients through use of the ReadyCleanse® cleansing cloths is minimal. In terms of benefit, it is possible that patients in this study may directly receive a benefit. The majority of satellite hospitals within the main site currently use soap-and-water for their catheter care and maintenance, which has the potential to become contaminated and transfer bacteria to the patient,

especially when the cleansing is not done in a standardized, systematic way. If the use of ReadyCleanse® cloths and the cleansing process described on label does reduce CAUTI, as is hypothesized, many patients in the study may have had a CAUTI prevented. Additionally, the reduction of CAUTI with the use of ReadyCleanse® could further develop global best practices for catheter care and maintenance to avoid CAUTIs. In sum, the benefits in this study outweigh the minimal risk presented to participants in the study.

3. OBJECTIVES AND ENDPOINTS

OBJECTIVES	ENDPOINTS	JUSTIFICATION FOR ENDPOINTS
Primary		
Evaluate if ReadyCleanse® cleansing cloths reduce CAUTI when used to perform catheter care and maintenance.	The primary endpoint will be incidence of CAUTI, measured per 1000 catheter days. The rate during the intervention will be compared to the historical rate for the facilities for the period preceding the intervention.	This endpoint was chosen as it is a direct measure of the objective of the study, using well-accepted criteria.
Secondary		
Evaluate if use of ReadyCleanse® cloths reduces bacteria counts in urine. This may provide a mechanistic account of any reduction in CAUTI.	Number of colony forming units (cfu/ml) of bacteria in urine from a random sub-sample of participants in the intervention, compared to a random sample collected prior to the intervention beginning.	This endpoint is a direct measure the objective, using well-accepted methodology.
Exploratory		
Evaluate the financial impact of using ReadyCleanse® cloths as the standard-of-care for catheter care and maintenance.	Cost savings in dollars through avoided CAUTIs, taking into account the cost of the product over the standard-of-care.	Common measure of financial savings used in Health Economics Outcomes Research
Gain feedback from healthcare professionals on the use of the product.	Healthcare professionals who administer the intervention will be asked to fill out a questionnaire (Appendix 11.2) about their experience with the product. Mean values from a four-choice scale will be computed for descriptive purposes.	Common survey approach to eliciting feedback on preferences.

## **4. STUDY DESIGN AND INTERVENTION**

### **4.1. Overall Design**

This is an open-label, superiority study intended to determine if IUC care and maintenance with a prepackaged cloth and standardized cleansing process (ReadyCleanse® Meatal and Perineal Cleansing Cloth) can reduce CAUTI relative to standard-of-care. Four northern suburban Chicago acute-care hospitals, all within the same system (NorthShore University Health System), will implement ReadyCleanse® as the standard-of-care for catheter care and maintenance. An initial training period of six weeks will first occur, during which medical staff will be trained on the appropriate use of the product, and have several weeks to become accustomed to it. Following this six-week training period, data will be collected on incidence of CAUTI prospectively for the duration until all expected catheter days (42,672) have been completed. The incidence rate of CAUTI during the intervention period will be compared to the incidence rate for a similar number of catheter days prior to the six-week training period. A significant reduction in CAUTI rate during the intervention period will be taken as evidence of the ReadyCleanse® cloths and standardized cleansing process likely reducing CAUTI. The end of the study will coincide with the 42,672 catheter days, at which point the study should be adequately powered (see Section 8).

The choice of using a retrospective control was due to balancing the need for a high volume of catheter days in order to adequately power the study, and conducting the study in a reasonable timeframe (see section 8). During the intervention period, all four hospitals will continue using their baseline CAUTI bundle prevention measures, and no additional new interventions will take place during the study period. Also, given that this study is using the ReadyCleanse® cloths per their intended use and implementing the intervention simultaneously across the entire hospital system, it takes the form of a quality improvement initiative whereby the use of a retrospective control is commonly used. Nonetheless, conclusions drawn from this study will emphasize the intervention as a whole, such as staff training on how to use the cloths, instructions for how often to use the cloth, as well as the properties of the ReadyCleanse® cloths and standardized cleansing process, in order to make the appropriate conclusion given the known limitations of the use of a retrospective control.

### **4.2. Investigational Product**

The intervention in this study will be the implementation of ReadyCleanse® cloths and the standardized cleansing process detailed on label as the new procedure for catheter care and maintenance across all four hospitals. This cloth is a currently marketed product which contains a pH-balanced, hypoallergenic solution. ReadyCleanse® cloths are specially designed for comprehensive meatal and perineal care to reduce the risk of developing a catheter-associated urinary tract infection (CAUTI). Each package contains five ReadyCleanse® cloths and a standardized cleansing protocol available on label. A copy of the product labeling and cleansing protocol is available in Appendix 11.1. Cleansing with ReadyCleanse® cloths and the standardized procedure will take place twice during a 24-hour period and after an incontinent episode.

### 4.3. Control Group

A retrospective control group will be used to compare the efficacy of the intervention. The standard-of-care for catheter care and maintenance at NorthShore hospitals is soap-and-water cleansing. Thus, the ReadyCleanse® cloth and cleansing process will be compared to soap-and-water cleansing. The ICU of one of the hospitals recently switched to using a different method for catheter care. Consequently, data from this unit will not be added to the retrospective dataset, but this unit will participate in the intervention and have their prospective data pooled with the other units and hospitals.

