**Figure 4.1**

Wash-in Period	ReadyCleanse® as standard care for all catheter care and maintenance at all four hospitals															
	1.5	2.5	3.5	4.5	5.5	6.5	7.5	8.5	9.5	10.5	11.5	12.5	13.5	14.5	15.5	16.5
Months																
*Study timeline may extend past 17.5 months. Study duration will be determined via completed catheter days (42, 672)																

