#### 6.3.1.2. Retrospective Data Collection

The CAUTI rate during the retrospective portion of the study is already collected; this rate will be compared to the CAUTI rate during the prospective portion of the study. Additionally, the CRF in 11.5 will be completed for any patient who had an IUC and developed a CAUTI in the similar number of catheter days as that of the intervention period, prior to the six-week training period. . These data will be extracted from the participants EHR from the sites electronic data warehouse and entered onto the CRF in the same fashion as the prospective data collection. Data from CRFs for participants in the retrospective arm will be transferred to the same electronic database as the prospective data for statistical analysis.

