## 8. STATISTICAL CONSIDERATIONS

### 8.1. Sample Size Determination

The primary outcome will be measured as number of CAUTIs per 1000 catheter days. Given this type of data, a Poisson regression model will be used to model CAUTI incidence, with the dichotomous predictor variable pertaining to the intervention serving as the critical test for the hypothesis. To determine how many catheter days would be needed to adequately power the study, a power analysis was conducted using G\*Power 3.1.9.2, with the following parameters:

- **Baseline CAUTI Rate:** 0.89/1000 catheter days (entered as .00089/day)
  - Baseline rate reflects CAUTI rate for NorthShore University Health System in 2016.
- **Hypothesized reduction in CAUTI:** 50%
- **Alpha:** 0.05 (one-tailed)
- **Power:** 80%
- **Mean Exposure:** 1 day (the actual exposure will vary by participant, but entering 1 day can be used to determine number of catheter days rather than number of participants).
- **R^2 other X:** 0%
- **X distribution:** Binomial
- **X parm II:** 0.5

The result from this analysis indicated that 83,426 catheter days would be needed to adequately power the study at 80%. NorthShore Hospital University System averages approximately 32,000 catheter days annually, which can be reduced to 2,667 per month. Thus, total number of catheter days required for collecting retrospective data and prospective data would be 85,344 catheter days. The 42,672 (85,344-catheter days/2) catheter days of prospective data in comparison to a similar number of catheter days of retrospective data will provide data required for conducting the analysis.

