## 8.2. Statistical Analysis

### 8.2.1. Primary Endpoint

The primary endpoint will be the comparison of CAUTI rates during the intervention period compared to the retrospective control period. This will be tested by modeling the likelihood of developing a CAUTI as a function of intervention status using Poisson regression, with the number of catheter days serving as the offset. A significant value for the parameter representing the intervention will serve as the test for the impact of the intervention. Formally, the hypothesis is:

$$H_0: \beta_1 \geq 0$$

$$H_1: \beta_1 < 0$$

Where  $\beta_1$  represents the beta-parameter for the dichotomous predictor variable pertaining to the intervention, with the retrospective control group coded as 0 and the prospective intervention group coded as 1.

The 95% confidence interval for the incidence rate ratio will also be presented.

Given that the retrospective and prospective portions of the study cover a significant period of catheter days, it is not expected that the two groups will vary on demographic variables or other key variables such as length-of-time the catheter is inserted, hospital unit during admission, etc. Thus, testing the incidence rate ratio will be sufficient for determining if there is a significant difference in the CAUTI rate between the two time periods.

In the event of over-dispersion of the data, negative binomial regression may be implemented to account for the over-dispersed data. Missing data on the primary endpoint is not anticipated to be a concern, given that government reporting requirements dictate that CAUTI rates be reported, which only requires an analysis of catheter days and number of CAUTIs. Participants who are discharged with an IUC or who expire during their admission will have their catheter days as well as any infections that occurred prior to discharge or death counted in the analysis.

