#### 9.1.7. Data handling and Record Keeping

##### 9.1.7.1 Data Collection and Management Responsibilities

Data collection is the responsibility of the clinical trial staff at the site under the supervision of the site investigator. The investigator is responsible for ensuring the accuracy, completeness, legibility, and timeliness of the data reported.

All source documents of any kind (electronic, paper, etc.) should be completed in accordance with Good Documentation Practices (GDP) to ensure accurate interpretation of data. CRFs will be created for each subject for the prospective portion of the study. CRFs will be generated retrospectively only for patients that developed a CAUTI. The CRF for each subject will be populated from the subject's EHR. The CRA will verify the data entered into the CRF with the site source regardless of the type of source. The site will be responsible for developing a written process that ensures the CRA is able view the source data.

Data from the CRFs will be entered by NorthShore study staff into a Microsoft Excel spreadsheet for statistical analysis. Data in the Excel database will be transferred to and analyzed with SAS, which allows for internal quality checks, such as automatic range checks, to identify data that appear inconsistent, incomplete, or inaccurate. Medline Industries, Inc. will be responsible for overseeing final data analysis and confirmation of results.

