**11.5. Case Report Form (CRF)**

R17-019 Case Report Form		Completed by:	
Demographic Information			
1. Participant Number:	2. Age:	3. Sex: Male  Female 	4. Race (may select more than one): Black  White  Asian  Hispanic  Other 
5. Hospital: E:  G:  S:  H: 	6. Room Number:		
Study Data			
1. Admission Date: (DD-MMM-YYYY)			
2. Date of catheter insertion (DD-MMM-YYYY)			
3. Date of catheter removal (DD-MMM-YYYY)			
4. Number of catheter days:			
5. Indication for catheter:		Open perineal wound:  Urinary obstruction/retention:  Pre- and Post-operative catheterization:  Complicated Urologic procedure:  Accurate measurement of urine output:  Other: 	
6. Did participant develop a CAUTI? (If yes, complete back side of form)		Yes:  No: 	
7. Did participant experience an AE or SAE (if yes, complete appropriate AE/SAE form)		Yes:  No: 	
Additional Data on Participants who Developed a CAUTI			
1. Date of CAUTI: (DD-MMM-YYYY)			
2. Patient arrived from:		Home:  Hospital:  LTCF: 	
3. Primary admission diagnosis:			
4. Did reason for catheter insertion meet CDC insertion criteria?		Yes:  No: 	
5. Did patient have fever > 100.4°F twice within 48 hours ?		Yes:  No: 	

ReadyCleanse vs SOC on CAUTI Rates  
 Medline Industries, Inc.  
 R17-019 Version 5.0

ALL MATERIAL INCLUDED IN THIS PROTOCOL IS CONFIDENTIAL

6. Was patient's white blood cell count $\geq$ 12,000?	Yes:  No: 
7. Did patient have flank pain?	Yes:  No: 
8. Did patient have dysuria or frequency after catheter removal?	Yes:  No: 
9. Date of urine culture (DD-MMM-YYYY)	
10. Reason for urine culture	

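### One hospital's ICU is excluded from the retrospective control but pooled into the intervention period, so the unadjusted rate ratio compares different sets of units

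*Combined protocol and SAP*

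**What the plan says.** Section 4.3 sets soap-and-water cleansing as the comparator. One hospital's ICU had recently changed its method, so "data from this unit will not be added to the retrospective dataset". On the intervention side the same section says "this unit will participate in the intervention and have their prospective data pooled with the other units and hospitals".

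Section 8.2.1 specifies a Poisson regression with intervention status as the only named predictor and catheter days as the offset. It argues that no adjustment is needed because the two groups should not differ on demographics or other key variables. The end of that list and the conclusion drawn from it read: "hospital unit during admission, etc. Thus, testing the incidence rate ratio will be sufficient for determining" whether the rates differ.

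On data sources, section 6.3.1.2 says "The CAUTI rate during the retrospective portion of the study is already collected", and section 9.1.7.1 says "CRFs will be generated retrospectively only for patients that developed a CAUTI". The case report form in Appendix 11.5 has one room-number field and one total, "4. Number of catheter days".

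The sample size in section 8.1 uses 0.89 CAUTIs per 1000 catheter days, with the note "Baseline rate reflects CAUTI rate for NorthShore University Health System in 2016". It does not say whether this ICU is included in that figure.

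**The concern.** Leaving the ICU out of the control is disclosed and reasoned. The gap is on the prospective side: the ICU's catheter days and infections enter the intervention period with no counterpart in the control period. Hospital unit is one of the variables on which 8.2.1 rests its case for not adjusting, and it is the one on which the plan itself guarantees a difference. The documents contain no unit term, no stratification and no analysis without this ICU. Section 4.1 acknowledges the general limits of a retrospective control but not this imbalance.

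If the ICU's underlying rate differs from that of the other units, the period effect mixes product effect with unit mix. A higher-rate ICU hides part of a real reduction; a lower-rate ICU produces an apparent reduction. Only about 38 control and 19 intervention events are expected and planned power is close to 80%, so a shift of a few percent in the rate ratio matters. The financial analysis in 8.2.3.2 counts avoided CAUTIs and would carry the same distortion if it uses the pooled rates.

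**Working it through.** **Inputs from section 8.1.** Baseline rate 0.00089 per catheter day; 50% reduction; one-sided alpha 0.05; 80% power; equal split; 42,672 catheter days per period; about 32,000 catheter days a year, or 2,667 a month.

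**The plan's own figure.** For a two-group Poisson Wald test, N = (z_α√V0 + z_β√V1)² / (ln 0.5)².

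- V1 = 1/(0.5 × 0.00089) + 1/(0.5 × 0.000445) = 6,741.6
- V0, at the geometric-mean rate 0.00089 × √0.5 = 0.000629, is 1/(0.25 × 0.000629) ≈ 6,356
- N = (1.645 × 79.73 + 0.842 × 82.11)² / 0.4805 ≈ 83,453

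The plan states 83,426, so its arithmetic is not at fault. Expected events are 42,672 × 0.00089 = 37.98 in the control period and 18.99 in the intervention period.

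**Composition effect.** Let s be the ICU's share of prospective catheter days and k its underlying rate relative to the other units, with the same product effect in every unit. Then

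observed rate ratio = true rate ratio × [1 + s(k − 1)].

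The documents give neither s nor k; all values below are assumptions. For scale, s × 32,000/365 is about 4.4 catheterised patients a day in that ICU at s = 5% and 8.8 at s = 10%.

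**Pooled analysis as planned.** I enumerated two independent Poisson counts, with control mean 37.98 and prospective mean 37.98 × [1 + s(k − 1)] × effect. The effect is 1 for type I error and 0.5 for power. The test is the one-sided 0.05 Wald test of the log rate ratio, with zero counts set to 0.5.

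| s | k | Multiplier | Type I error | Power |
|---|---|---|---|---|
| any | 1 | 1.000 | 4.9% | 81.5% |
| 5% | 0.5 | 0.975 | 6.1% | – |
| 5% | 1.5 | 1.025 | 3.9% | 79.4% |
| 5% | 2 | 1.05 | 3.1% | 77.2% |
| 10% | 0.5 | 0.95 | 7.5% | – |
| 10% | 1.5 | 1.05 | 3.1% | 77.2% |
| 10% | 2 | 1.10 | 1.9% | 72.4% |

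A normal approximation gives similar results: 79.4% power with no imbalance, and at s = 10%, 70.9% power for k = 2 and 7.7% type I error for k = 0.5.

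**Restricted to units in both periods.** Prospective days and mean are multiplied by (1 − s). Type I error stays at 4.8–4.9% whatever k is. Power without extra days is 80.2% at s = 5%, 79.2% at 10% and 76.4% at 20%.

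**If 0.89 already includes the ICU.** The rate in the other units is then 0.89/[1 + s(k − 1)]. At k = 2 that is 0.89/1.05 = 0.848 (s = 5%) or 0.89/1.10 = 0.809 (s = 10%) per 1000. Pooled power at k = 2 is 75.4% and 68.8%, against 78.5% and 75.5% when restricted.

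**The case against.** The strongest reply is that the harm is hypothetical and the remedy not free. Both s and k are assumed. A false-positive problem needs k below 1, and the documents give no reason to expect that; otherwise the error is conservative. At k = 1 restriction only loses power: 81.5% to 80.2% at s = 5%, or to 79.2% at s = 10%. At k = 1.5 the gain is small: 79.4% against 80.2%, and 77.2% against 79.2%. If the ICU holds only 2% of days, type I error is 5.3% at k = 0.5 and power is 79.8% at k = 2, so little changes. Sections 4.1 and 4.3 also describe a system-wide initiative and disclose the pooling. On that view a common-units sensitivity analysis and one corrected sentence would be enough.

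The point about size stands: the effect may be small and is zero at k = 1. But a sensitivity analysis alone leaves the primary test exposed to whatever s and k turn out to be, while restriction holds the type I error near nominal for every k. Restriction also follows 4.3's own rationale: ReadyCleanse is to be compared with soap-and-water, and this ICU has no soap-and-water data in the comparison.

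Two smaller points are fair. Prospective data come from the electronic health record as well as the form, so an approximate prospective split by unit is obtainable. The CAUTI definition is deferred to a CDC document not reproduced in the protocol, so whether it settles infection attribution on transfer cannot be judged here. Attribution of catheter days remains unstated.

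**Conclusion.** The concern holds. Sections 4.3 and 8.2.1 conflict, and the stated reason for an unadjusted comparison fails on a variable whose imbalance is known in advance. Direction and size cannot be fixed from the documents: the bias is zero at k = 1, conservative with lost power at k above 1, and anti-conservative only at k below 1. Over the assumed s of 5–10% and k of 0.5–2, type I error runs from 1.9% to 7.5% against 4.9% without imbalance, and power falls to as low as 72.4% from 81.5% (68.8% if the 0.89 baseline includes the ICU). These figures assume a common product effect across units and Poisson counts without over-dispersion. The conflict in the text is certain; a material bias is possible but not shown. This should be fixed.

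**What to change.** 1. In 4.3 and 8.2.1, restrict the primary Poisson comparison to units that contribute to both periods, and report the all-units pooled result as a sensitivity analysis. No new retrospective data are needed, since the ICU is already absent there. Record that the change was made before any look at outcome data, as the document history does for the version 4.0 analysis change.
2. Correct the statement in 8.2.1 that hospital unit is not expected to differ between periods.
3. State how prospective catheter days and CAUTIs are attributed for patients who move into or out of this ICU, using the same rule by which the ICU was removed from the retrospective rate. The case report form cannot supply this, with one room field, one catheter-day total and retrospective forms for CAUTI cases only. Unit-level prospective days must come from the electronic health record.
4. Either restate power for the reduced prospective days, or count 42,672 days on the retained units. Say whether the 0.89 baseline includes this ICU.

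The cost is wording, a written transfer rule and an extract of prospective days by unit. Without a top-up, power is about 80.2% (s = 5%), 79.2% (10%) or 76.4% (20%). With a top-up, the extra days are 42,672/(1 − s) − 42,672: about 2,246 at s = 5% (2,246/2,667 = 0.8 month) or 4,741 at s = 10% (1.8 months).
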